10.1.11 Publication and Data Sharing Policy	
10.1.12 Conflict of Interest Policy	
10.2 Additional Considerations	
10.3 Abbreviations and Special Terms	
10.4 Protocol Amendment History	
11 REFERENCES	

The trial will be carried out in accordance with International Council on Harmonisation Good Clinical Practice (ICH GCP) and the following:

United States (US) Code of Federal Regulations (CFR) applicable to clinical studies (45 CFR Part 46, 21 CFR Part 50, 21 CFR Part 56, 21 CFR Part 312, and/or 21 CFR Part 812).

National Institutes of Health (NIH)-funded investigators and clinical trial site staff who are responsible for the conduct, management, or oversight of NIH-funded clinical trials have completed Human Subjects Protection and ICH GCP Training.

The protocol, informed consent form(s), recruitment materials, and all participant materials will be submitted to the IRB for review and approval. Approval of both the protocol and the consent form(s) must be obtained before any participant is consented. Any amendment to the protocol will require review and approval by the IRB before the changes are implemented to the study. All changes to the consent form(s) will be IRB approved; a determination will be made regarding whether a new consent needs to be obtained from participants who provided consent, using a previously approved consent form.

# PLANTS Pilot Trial Protocol STUDY21080178 1 PROTOCOL SUMMARY

#### **Synopsis** 1.1

Title	Draviding LODTO, Adalassanta with Numberson Tructure thisses, and Osfette
Title:	Providing LGBTQ+ Adolescents with Nurturance, Trustworthiness, and Safety (PLANTS): Pilot Cluster-Randomized Controlled Trial
Grant Number:	K01AA027564
Study Description:	This pilot cluster-randomized controlled trial will evaluate the PLANTS (Providing LGBTQ+ Adolescents with Nurturance, Trustworthiness, and Safety) course among high school staff. The primary hypotheses are that the PLANTS course will have high acceptability, usability, appropriateness, and feasibility as reported by high school staff.
Objectives:	
 
Primary Objective: 
 
For high school staff, is PLANTS acceptable, usable, appropriate, and feasible?
 
Secondary Objectives: 
 
To what extent was the PLANTS course and trial successfully implemented and safe for high school staff and schools?
 
Among high school staff participants in the PLANTS arm, do they report pre-post improvements in active-empathic listening, self-efficacy for supporting, affirming,
 
 
 
 
 

	and protecting sexual and gender minority youths, and positive bystander intervention behaviors for bullying? -Among high school staff, is the PLANTS intervention more efficacious in improving their active-empathic listening, self-efficacy for supporting, affirming, and protecting SGMY, and positive bystander intervention behaviors for bullying than an email intervention of publicly available resources?
Endpoints:	Primary Endpoints: Intervention acceptability, usability, appropriateness, and feasibility. Secondary Endpoints: Intervention efficacy for school staff; Success of intervention implementation; Success of trial implementation; Intervention safety.
Study Population:	The primary study population is high school staff, aged 18 years old and over, who work at high schools in the MetroWest Region outside Boston, Massachusetts.
Phase or Stage:	Pilot Phase
Description of Sites Enrolling Participants:	This is a single site study conducted by the University of Pittsburgh.
Description of Study	The PLANTS (Providing LGBTQ+ Adolescents with Nurturance, Trustworthiness,
Intervention:	and Safety) intervention course is a community-informed, theory-based intervention for training high school staff to better support, affirm, and protect SGMY. The intervention is web-based, containing self-paced asynchronous modules and synchronous group-based events. The intervention will occur across a period of three months.
Study Duration:	The estimated study duration is 12 months.
Participant Duration:	High school staff will complete all study-related tasks within 9-12 months.

#### Study Flow of Two-Arm Cluster-Randomized Controlled PLANTS Pilot Trial, Nested within the MetroWest Adolescent Health Survey Infrastructure

#### PLANTS Pilot Trial Protocol STUDY21080178 **1.3 Schedule of Activities**

	School Screener	Staff Screener (Time 0)	Staff Baseline Survey (Time 1)	PLANTS Program	Control Program	Staff Follow-up Survey (Time 2)	Staff Follow-up Interview (Time 3)
SCHOOL DATA							
Inclusion/exclusion	Х						
Public school data	Х						
Randomization	Х						
STAFF DATA							
Inclusion/exclusion		X X					
Informed consent		Х					
Demographics			Х			Х	
Social desirability			Х			x	
bias			^			^	
Existing school			х			x	
programs			^			^	
Primary Outcomes							
Intervention Acceptability, Usability, Appropriateness, and Feasibility				х		x	x
Secondary							
Outcomes							
Implementation Outcomes	Х	Х	Х	Х	Х	x	Х
Adverse Events Reporting			Х	Х	Х	х	х
Active Empathetic Listening			Х	Х		Х	Х
Self-efficacy for			Х	Х		х	х
Working with SGMY Self-efficacy of PLANTS' Change			х	х		x	x
Objectives Bystander Intervention Behaviors for Bullying			х	х		x	x

# 2 INTRODUCTION

### 2.1 Study Rationale

#### Statement of the Problem

Sexual and gender minority youth (SGMY; i.e., adolescents who identify as gay/lesbian or bisexual, who have same-gender sexual behaviors or attractions, who identify as transgender or nonbinary, or whose gender identity do match their sex assigned at birth) are at significantly higher risk than their heterosexual peers for using drugs (tobacco and marijuana) and alcohol. Alcohol use is 123-155% higher among sexual minority youth than heterosexual youth and up to 250% higher among gender minority youth than cisgender youth. SGMY are more likely to drink alcohol at earlier ages. For U.S. teens in 9th grade, binge drinking (4+/5+ drinks within 2 hours) was higher among gays/bisexuals vs. heterosexuals (13% vs. 7%) and those with same-gender sexual behaviors vs. heterosexually-behaving youth (28% vs. 16%). These substantial and persistent inequities make SGMY a priority population for interventions that reduce drug and alcohol use; thus, intervention research for SGMY was deemed a priority by national health agencies. However, there are few efficacious alcohol/drug use interventions for SGMY.

#### Rationale Underlying the Intervention

One way to reduce alcohol and drug use for SGMY is to foster more supportive and inclusive high school environments by training school staff (e.g., teachers, principals, nurses, counselors) to effectively support and protect SGMY. SGMY who have support from adults at school, greater school connectedness, and lower bullying victimization also have reduced depressive symptoms, suicidality, drug use, and alcohol use. Unfortunately, SGMY are more likely than their heterosexual peers to lack supportive adults at school, have lower school connectedness, and to be victims of bullying. An intervention that trains school staff to better understand and support SGMY and engage in positive bystander behaviors that protect SGMY from bullying victimization may reduce sexual-orientation disparities in drug and alcohol use. An intervention for school staff is further warranted because the presence of gay-straight alliances and SGMY-inclusive school policies fail to eliminate sexual-orientation drug and alcohol disparities. This is likely due to school staff's lack of knowledge, skills, and self-efficacy about supporting SGMY—and their lack of training on SGMY.

#### Study Intervention: PLANTS Course

The intervention being studied, PLANTS (Providing LGBTQ+ Adolescents with Nurturance, Trustworthiness, and Safety), is an online-delivered training program, including asynchronous and synchronous activities targeting high school staff. This intervention is informed by the Information-Motivation-Behavior theory to target high school staffs' skills, self-efficacy, knowledge, and outcome expectations. Members of the study population as well as collaborators invested in SGMY well-being provided valuable feedback on PLANTS throughout its development.

Regarding the intervention's targeted behavioral outcomes, upon completion of the PLANTS program, high school staff will: provide interpersonal support and affirmation to SGMY; provide educational resources that are inclusive of SGMY; provide safe spaces for SGMY; promote acceptance of SGMY among cisgender heterosexual youth; prevent and reduce bullying, cyberbullying, and harassment of SGMY; evaluate and advocate for SGMY inclusivity and protections in school policies; and maintain the confidentiality of SGMY. By having high school staff achieve these behavioral outcomes, we hypothesize that SGMY will experience less

# PLANTS Pilot Trial Version 1.0 Protocol STUDY21080178 2024.04.05 risk factors (e.g., bullying victimization) and more protective factors (e.g., school-based adult support), which will in turn reduce SGMY's substance use and mental health problems.

#### Rationale for the Clinical Trial

The primary aim of this clinical trial is to rigorously test the acceptability, usability, appropriateness, and feasibility of the PLANTS intervention using a 2-armed cluster-randomized controlled trial. We will also examine the efficacy of intervention in improving high school staff outcomes as well as implementation and safety outcomes related to the intervention and trial. Results from this pilot trial will provide necessary information to conduct a fully powered trial of the efficacy of PLANTS for reducing the ultimate health outcome of SGMY alcohol use.

#### 2.2 Background

SGMY health equity intervention research is a priority of many major organizations, including NIH, Healthy People 2030, and the National Academy of Medicine (formerly the Institute of Medicine). To date, little NIH-funded intervention research for sexual minority populations has focused on drug and alcohol use. As shown by the IOM and a systematic review we conducted, there exist few efficacious interventions aimed at reducing drug and alcohol use for SGMY. Our systematic review of the peer-reviewed literature found only one alcohol/drug use intervention for SGMY, which was an individual-level intervention with no improvements in alcohol, tobacco, or marijuana use. Furthermore, the rigor of SGMY all of which are addressed in this study.

Despite the lack of SGMY intervention research, a robust body of theoretic and empirical research shows SGMY disparities in alcohol/drug use and mental health are driven by sexuality- and gender-based stigma. Stigma has the dual effect of reducing stigmatized populations' access to important protective factors (such as adult support) while increasing their experiences of risk factors (such as discrimination). Thus, reducing sexuality- and gender-based stigma is an essential component of interventions to effectively reduce SGMY drug and alcohol disparities. However, sexuality- and gender-based stigma reduction is commonly absent in traditional drug/alcohol use programs, highlighting the need for new SGMY-specific interventions.

Schools provide an ideal setting for SGMY-specific interventions to reduce drug and alcohol use disparities. High school students spend ~1,195 hours per year in school, providing an ideal place to reach SGMY. SGMY regularly interact with adults, including school teachers, principals, nurses, counselors, and social workers, who are professionally bound by certifying bodies to support the needs of students, including SGMY. Nevertheless, implementing interventions in schools is challenging because of schools' limited resources, increasing demands placed on teachers, and difficulty in acquiring school buy-in. These barriers can be overcome by using economical and easily implementable interventions, such as online programs, and developing interventions and implementation strategies in collaboration with school collaborators.

School-based interventions can build upon epidemiologic research identifying factors associated with sexualorientation disparities in drug and alcohol use. For example, SGMY are more likely than cisgender heterosexuals to experience bullying victimization in school, which is associated with greater and mental health problems and alcohol/drug use for SGMY. Compared with heterosexual youth, SGMY report lower prevalence of adult support at school and reduced school connectedness, which is associated with better mental health and lower drug and alcohol use. Therefore, school-based

# PLANTS Pilot Trial Version 1.0 Protocol STUDY21080178 2024.04.05 interventions aimed at reducing risk factors and increasing protective factors for SGMY will likely reduce their drug and alcohol use disparities.

In particular, training school staff (e.g., teachers, principals, nurses, counselors) to support, affirm, and protect SGMY is hypothesized to reduce bullying victimization, increase school support and connectedness, and mitigate SGMY drug and alcohol use. Unfortunately, school staff often lack the necessary training to effectively support, affirm, and protect SGMY. Many school staff have a strong desire to support SGMY. However, they report the primary barrier to supporting SGMY is their lack of training. In 2014, only 13% of teachers across the U.S. received training on SGMY-related issues, and only 29% in Massachsuetts, highlighting the need for SGMY-related professional development training in schools. Offering the free and easily accessible online PLANTS intervention to school staff is hypothesized to be beneficial for school staff and for reducing disparities in drug and alcohol use for SGMY.

# 2.3 Risk/Benefit Assessment

# 2.3.1 Known Potential Risks

Immediate potential risks:

- Breach of confidentiality
- Emotional discomfort
- Backlash from people for supporting SGMY

Long-term potential risks:

- Breach of confidentiality
- Emotional discomfort
- Backlash from people for supporting SGMY

#### 2.3.2 Known Potential Benefits

Immediate potential benefits

Improved interpersonal relationships with SGMY

Long-term potential benefits

- Improved interpersonal relationships with SGMY
- This study is highly significant because we currently have limited promotion and prevention programs for SGMY. Therefore, the benefit of this systematic program evaluation is that the findings may add to the evidence base of violence prevention programs available to help improve health for SGMY.

#### 2.3.3 Assessment of Potential Risks and Benefits

This is a minimal risk study because the risks that could occur from participation in the intervention or trial are unlikely. Furthermore, we have taken several precautions to minimize potential risks.

Breach of Confidentiality: It is possible that breach of confidentiality may occur. However, we have taken the following active steps to minimize the likelihood of breach of confidentiality. First, all surveys are collected electronically via REDCap, a secure web application for building and managing online surveys and databases.

While REDCap can be used to collect virtually any type of data (including 21 CFR Part 11, FISMA, and HIPAAcompliant environments), it is specifically geared to support online data capture for research studies and operations. Second, we ask that you complete the survey in a private place where no one can see your answers. Surveys can be completed on any computer, tablet, or mobile device, allowing you to complete the surveys when they feel most comfortable. Third, only our research team will have access to REDCap. We will never share their individual answers with any other school staff or administrators. Fourth, for interviews, we will use HIPAA-compliant Zoom accounts and ask that interviews be taken in private quiet spaces. Together, these procedures mitigate the risk of breach of confidentiality.

Emotional discomfort: It is possible that some participants may experience emotional discomfort, embarrassment, or distress while answering questions or as a result of intervention/control materials. We take the following precautions to protect subjects. First, you do not have to answer any question that makes you uncomfortable or that you do not understand. Second, participation in this study is completely voluntary. Third, we will not be asking you questions about sensitive traumatic experiences that may have happened to them. Together, these procedures mitigate the risk of emotional discomfort for school staff.

Backlash from people for supporting SGMY: It is possible that some participants may experience backlash, but it is unlikely. We take the following precautions to protect subjects from backlash. First, PLANTS encourages high school staff to consider their sociopolitical environments before implementing strategies to support SGMY. Second, all strategies in PLANTS are suggestions; school staff are not required to implement any strategies they do not want to. Third, all information reported in our study are completely confidential; we never share identifiable information with anyone outside the study team. Fourth, we will only enroll high school staff from schools that agree to participate in the trial, increasing the likelihood that school leadership is in favor of supporting SGMY and minimizing potential backlash.

Overall, this is a minimal risk study: all risks are unlikely to occur, and we provide high school staff with suggestions on how to prevent them from happening when they are within their control. Because we currently have limited scientific evidence about programs that aim to train high school staff to support, affirm, and protect SGMY, the potential benefits of this systematic program implementation far outweigh the minimal risks associated with the study.

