#### PLANTS Pilot Trial Version 1.0 Protocol STUDY21080178 2024.04.05 **OBJECTIVES ENDPOINTS** JUSTIFICATION FOR ENDPOINTS To assess PLANTS -PLANTS participation rate These measures assess school implementation -PLANTS completion rate staff's implementation and uptake of -Participation rate in live Zoom events the PLANTS intervention. To assess trial -Participation rate These measures assess the success implementation -Attrition rate of the pilot trial in reaching an -Intervention demand adequate number of school staff. To determine the -Parent backlash Although we anticipate the incidence safety of PLANTS -Social media backlash of these adverse events to be low. they are the most common and could -School board backlash be most harmful to school staff. -Suspension or removal from employment -Censorship of LGBTQ+ literature/history/stories or removal of books with LGBTQ+ representation from school libraries.

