# 6.1.2 Administration and Dosing

PLANTS online modules will be administered online via Canvas. Sections will be opened once per month, and there are a total of 3 sections over 3 months. The synchronous Live Events will be administered via Zoom. There are a total of 3 events. A "Full Dose" of the PLANTS intervention includes completion of all the online modules and 3 Live Zoom Events. The Live Zoom Events are required to be administered by trained interventionists (the PI or Research Assistants). In the Live Zoom Events, participants will interact with each other and a shared interventionist in a virtual environment. Active control materials cannot be tracked as easily

because these online trainings are administered via other agency's websites (not the study team's website). There are no interventionists in the active control arm.

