# 6.2 Fidelity

### 6.2.1 Interventionist Training and Tracking

The PLANTS Live Zoom Events require effort be made to check that the intervention is appropriately conducted by the interventionists. For each Live Zoom Event, the research assistant(s) will keep detailed notes of the sessions. We will then check these notes against the change methods and learning objectives for each module to ensure fidelity of the intervention. We will also monitor implementation of the PLANTS asynchronous online modules by checking that the release dates are met in the online platform. We use Canvas Learning Management Software to deliver PLANTS. We will monitor intervention compliance and fidelity via module questionnaires, Canvas informatics, event attendance, and follow-up survey questionnaires.

EMAILS has no direct human interaction in this intervention other than email. We will track delivery of EMAILS by checking sent emails against an implementation plan. We will monitor active control compliance and fidelity via email clicks by sending emails with training links from Qualtrics to participants, and then participants click on the training links in Qualtrics for tracking purposes. We will also use follow-up survey questionnaires to assess use of EMAILS.

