#### 8.2 Safety Assessments

In each staff survey, we will assess the following variables. In addition to the questions below, we will also leave open-ended text boxes so people can provide more detail on the incident.

Variables	Description	Levels/range	Justification
Parent backlash	Contact from disgruntled parents/guardians of students because LGBTQ+ inclusivity is in the classroom	Yes/no + Frequency	Parents may not be comfortable with the education their children are receiving and ask questions that educators may not be comfortable or feel safe answering.
	People attack school staff or the school for supporting LGBTQ+ youth	Yes/no + Frequency	This is happening all over the country
School board backlash	School board gets upset or concerned about staff supporting LGBTQ+ youth	Yes/no + Frequency	This is happening all over the country
Suspension or removal from employment	•	Yes/no + Frequency	This is happening all over the country

PLANTS Pilot Trial Protocol STUDY21080	178		Version 1.0 2024.04.05
Censorship of	Promotion and integration of	Yes/no +	This is happening throughout the
-	LGBTQ+ issues, history,	frequency/quantity	country
literature/history/stories	stories into the school		
or removal of books	curriculum could lead to		
with LGBTQ+	attempts to censor that		
	information by parents, school		
	boards, and higher ups in the		
	education system. Oftentimes		
	this has been justified as		
	avoiding "controversial/political		
	topics" in schools. There is the		
	possibility that teachers who		
	teach about		
	"controversial/political" topics		
	could be silenced via threats of		
	losing their jobs.		
Emotional discomfort	Staff are uncomfortable with	Likert 5-point	Some topics may provoke
with PLANTS	the training program.	scale + Open-	discomfort.
		ended	

Study team members will have contact staff and will be able to report adverse events in the appropriate case report form. In the post-trial interviews, we will interview a subset of participants who reported experiencing adverse events. We will ask questions about the AE during interviews, which will help support knowledge of the study intervention effects. We will follow-up with individuals if the event is severe (see the MOP).

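### Breach of confidentiality is the first risk the protocol names, yet no safety endpoint or survey item asks about it, and its stated safeguards do not address the group Live Zoom Events

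*Combined protocol and SAP*

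**What the plan says.** Section 2.3.1 names three risks, each both immediate and long-term, and the first is "Breach of confidentiality". Section 2.3.3 says of it: "It is possible that breach of confidentiality may occur".

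Section 3 sets five safety endpoints: backlash from parents, on social media and from the school board; suspension or removal from employment; and censorship or book removal. Section 8.2 introduces its table with "In each staff survey, we will assess the following variables" and lists the same five plus emotional discomfort with PLANTS. It adds open text boxes for more detail about the incident.

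Section 2.3.3 gives four steps against a breach: surveys collected in REDCap, completing surveys in private, access limited to the research team, and a step for interviews: "Fourth, for interviews, we will use HIPAA-compliant Zoom accounts and ask that interviews be taken in private quiet spaces".

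Section 6.1.1 requires attendance at three Live Zoom Events. Section 6.1.2 says: "In the Live Zoom Events, participants will interact with each other and a shared interventionist in a virtual environment". Section 6.2.1 adds: "For each Live Zoom Event, the research assistant(s) will keep detailed notes of the sessions".

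Sections 9.1 and 9.4.4 judge safety by whether at most 20% of PLANTS participants report adverse events.

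**The concern.** A safety conclusion covers the harms that were looked for. Of the three risks the protocol itself names, breach is the only one with no measure of its own.

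One route to a breach also belongs to the PLANTS arm alone: a colleague repeating something said in a live event. EMAILS has no human contact other than email (Section 6.1.1). The study team could notice a leak of its own data, but it is poorly placed to notice a remark repeated at school unless the person affected reports it.

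The stake is limited but real. The 20% criterion can be met with no question specific to the first-listed risk, and the pilot would give the later full trial no estimate of how often it happens.

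**Working it through.** **1. Named risks against measures**

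| Risk in 2.3.1 | Section 3 safety endpoint | Section 8.2 survey item |
|---|---|---|
| Breach of confidentiality | none | none |
| Emotional discomfort | none | yes |
| Backlash | yes | yes |

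**2. Whether general provisions fill the gap**

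- *General solicitation (8.3.4).* Adverse events are to be solicited in surveys and interviews, with a generic question about problems at work as an example. A breach could surface here if the participant thinks of it as such a problem.
- *Open text boxes (8.2).* These are for detail on an incident, which points to the listed items.
- *Interviews.* They are optional (4.4). Section 8.2 plans adverse-event questions for a subset of those who already reported an event, and the interview domains in 8.1 do not include confidentiality.
- *Unanticipated problems (8.4.1).* Social and psychological harm is covered, but the event must also be unexpected given the protocol. A breach is named there, so an ordinary one may not qualify.
- *Adverse-event definition (8.3.1).* The wording is medical, while the severity grades in 8.3.3.1 refer to well-being at work, job loss and lawsuits. Whether a breach counts is unclear.
- *Privacy (9.5.3).* Research activities are to be held as privately as possible. This does not address what one participant hears from another.

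Each capture route exists, but none asks about a breach.

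**3. The plan's own figure**

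Section 9.2 gives a 95% confidence interval width of no more than 0.21 for the adverse-event proportion with n = 86. Taking the worst case p = 0.5:

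2 × 1.96 × √(0.25/86) = 0.2113, which rounds to 0.21. The figure reproduces.

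**4. What could move the 20% conclusion**

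With n = 86, the criterion is met up to 17/86 = 19.8% and fails at 18/86 = 20.9%. With the 65 follow-up completers assumed in 9.2, it is met up to 13/65 = 20.0% and fails at 14/65 = 21.5%.

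The documents give no rate for recorded events, so 5%, 10% and 15% are assumed. The further participants needed to cross 20%, each with a breach as their only event, are:

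| Assumed recorded rate | n = 86 | n = 65 |
|---|---|---|
| 5% | 18 − 4 = 14 | 14 − 3 = 11 |
| 10% | 18 − 9 = 9 | 14 − 6 = 8 |
| 15% | 18 − 13 = 5 | 14 − 10 = 4 |

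(10% of 65 is 6.5, taken as 6.)

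**5. What a direct item would add**

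If the item were asked and nobody reported a breach, the one-sided 95% upper limit would be 1 − 0.05^(1/65) = 4.5% with 65 responders, or 1 − 0.05^(1/86) = 3.4% with 86. This treats staff as independent, which is doubtful for a leak from a shared session, and it bounds only breaches that the person affected knows about. The current plan supports no such statement.

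**The case against.** The strongest reply is that the gap is narrower than it looks. Section 8.3.4 solicits adverse events generally and names Live Zoom events as a detection route, and 8.4 covers social harm. A reader might infer that this harm is never asked about. The documents do not support that; they show only that no question is specific to it.

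A reader might also infer that the reported proportion is too low by the full breach rate. That does not follow. The additional safety analyses in 9.4.4 count each participant once, and a breach that led to backlash, employment action or discomfort already has an item. Only a participant whose sole event is an uncaptured breach is lost.

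A third tempting reading is that the complete-confidentiality assurance in 2.3.3 is wrong because colleagues hear each other in live events. That assurance most naturally concerns data reported to the study team, and its next clause is about the team sharing identifiable information. It is not shown to be false.

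It is also fair that Section 3 justifies its list as the most common and potentially most harmful events, that a named risk need not be an endpoint (emotional discomfort is not one either), and that the documents do not say sensitive matters are disclosed in live events. A ground rule for those events may stand in the consent form or the manual of procedures, neither of which is available here.

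What remains is that emotional discomfort at least has a survey item and breach does not, and that capture depends on the participant raising it unprompted.

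**Conclusion.** The point holds as a measurement gap. Breach of confidentiality has no item of its own in Section 3 or Section 8.2, and the specific safeguards in 2.3.3 do not address the Live Zoom Events. The 9.4.4 proportion may omit participants whose only event is a breach.

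The size is unknown. It is zero if no breach occurs, or if every breach is reported or accompanied by another recorded event. Nothing in the documents shows that the omission would reverse the 20% conclusion: on the assumed recorded rates, that would take between 4 and 14 breach-only participants, depending on the rate and the denominator. The primary endpoints are untouched. This is a worthwhile, inexpensive improvement to a secondary safety outcome in a study the protocol regards as minimal risk.

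**What to change.** - Add one row to the Section 8.2 table and to the Section 3 safety endpoints: *Breach of confidentiality (something you shared in the study became known to others): yes/no + frequency.*
- Ask it in both arms and report it as its own line by arm. Count it in the 9.4.4 proportion, once per participant, and say there that it counts as an adverse event despite the medical wording of 8.3.1.
- Add a brief confidentiality statement for Live Zoom Events to 2.3.3, unless the consent form or manual of procedures already contains one.

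The cost is one survey item, one table row and, where needed, a sentence or two. The downside is that the reported event proportion may be slightly higher.
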